## 1.1.2 Trial/Study Registration

The trial will be registered on clinicaltrials.gov before enrolment of the first site. Wherever words denoting a specific gender are used in this protocol, they are intended to apply equally to all persons without regard to gender.

# 1.2 Synopsis

Title	A pilot study to test benefits of drinking clear fluids until called to the operating room in adult surgical patients.		
Short title	HYDRATE-Study		
Indication	Patients ≥ 18 years of age undergoing surgery without an indication for rapid sequence induction.		
Primary end point	
 
Primary efficacy endpoint:
 
Patient thirst (No; Yes, moderate; Yes, severe)
 
Endpoint will be measured prior to anaesthesia induction.
 
		
Secondary end points	Endpoint will be measured prior to anaesthesia induction.  Key secondary endpoints:  We will pilot test the intervention to demonstrate its acceptability and feasibility and to identify target outcomes for further trials.  Piloting for feasibility assessment:  Total number of protocol deviations per group  Outcome assessment successfully blinded  Real fluid fasting time is less than allocated fluid fasting time  Fluid fasting time		

	Piloting for future power calculations: Richmond Agitation Sedation Scale (RASS) Confusion Assessment Method for the Intensive Care Unit (CAM-ICU) Headache Vital signs (delta heart rate, delta blood pressure) Cumulative Vasopressor dose within 15 min after anaesthesia induction Blood glucose level Number of attempts for placing a peripheral intravenous catheter Postoperative nausea and vomiting (PONV)  Safety Endpoints: Unplanned intensive/intermediate care unit stay due to respiratory complications
	

Confirmed bronchopulmonary aspiration

Death within observation period

Trial design	The study is a prospective, single centre, outcome assessor
Trial population	blinded, controlled randomised clinical trial (RCT) with 3 arms.  Inclusion criteria on the individual level: Patients ≥ 18 years of age scheduled for surgery under anaesthesia care (general anaesthesia, regional anaesthesia, combined anaesthesia or monitored anaesthesia care) with an ASA physical status classification I-III.  Exclusion criteria: Absolute and relative indication for rapid sequence induction, dysphagia, renal replacement therapy, fluid restriction therapy, pregnancy, expected need for postoperative mechanical ventilation and prior enrolment in this trial.
Sample size	n = 174 (55 per group +5% drop-outs = 58 per group)
Study Procedures	Group 1 (control) - Usual care: Fasting instructions as given by anaesthesiologist according to national guidelines (6 h solid meal and thick liquids, 2 h clear fluids).  Group 2 (intervention) - Instructed guideline adherence: As per "Usual care". In addition, the operating room schedule is closely monitored and the patient will be visited to be supported and encouraged in drinking clear fluids freely until 2 h before the anticipated beginning of anaesthesia.  Group 3 (intervention) - Experimental intervention: As per "instructed guideline adherence" with the difference that the patient will be educated and encouraged to drink up to 200 ml clear fluids between 2 h prior to anaesthesia and the call to operation room. From this concludes that patients are allowed to drink up to 100 ml clear fluids every 1 h the anaesthesia is postponed.  Follow-up per patient: 2 h after discharge from the operating room (up to 48 h e.g. in case of bronchopulmonary aspiration).
Biometry	Analyses will be intention-to-treat. The primary endpoint will be analysed by standard methods of descriptive statistics, namely chisquare test.  The treatment effect will be quantified on the odds ratio scale with two-sided 95% confidence intervals provided. Secondarily, also point estimates and confidence intervals for the rate difference and the relative risk will be provided.  The overall trial will have 80% power (alpha=0.05)

Trial Duration	Duration of intervention: On the day of scheduled surgery until call to the operating room.
	Individual trial duration: From the day of scheduled surgery until up to 2 h after discharge from the operating room. Follow-up might be postponed up to 48 h e.g. in case of bronchopulmonary aspiration.
	Planned recruitment period: 3 months
	The trial formally starts with the treatment of the first patient (FPI = first patient in), and the formal end of the study is the last follow-up visit of the last patient included (LPO = last patient out). The total study duration will be 3 months.

[figure not shown]

Fig. 1: Possible courses through the study

## 1.2.1 Schedule of Assessments and Procedures

Examinations	Screening	Intervention	Prior to anaesthesia	After induction	Follow up
	28 days up to 0 days before surgery	On the day of surgery until call to the operating room	Immediately before anaesthesia induction	Immediately after anaesthesia induction	2 h (±30 min) after procedure a
Visit	V1	V2	V3	V4	V5
Inclusion criteria	X				
Exclusion criteria	X				
Informed consent	X				
Medical history b Baseline	Х				
assessments	х				
Registration	X				
Demographics	X				
Randomisation	Х				
Intervention		X			
Fasting time			(X) c		Х
IV-catheter placement			x		
Patient satisfaction			Х		Х
Blood glucose level			Х	(X) d	
Vital signs			Х	Х	
Use of vasopressors				Х	
Bronchopulmonary aspiration				X	X
Headache			X	^	X
PONV					X
RASS + CAM-ICU					X
Blinding successful			Х	Х	Х

<sup>aFor general anaesthesia this is 2 h after extubation. For regional anaesthesia this is 2 h after skin suture. Parts of Follow up might be postponed up to 48 h e.g. if bronchopulmonary aspiration is to be confirmed.

<sup>bThe premedication visit will be added to the study documentation to record the inclusion and exclusion criteria.

<sup>cFluid fasting time must be greater than 30 minutes at anaesthesia induction. The actual fasting time will be assessed at the end of V5 to ensure outcome assessor blinding. dOnly if not done at V4.

## 1.2.2 Study Flow Chart

# Inclusion criteria: Patients ≥ 18 years of age · Scheduled for surgery under anaesthesia care · general anaesthesia, regional anaesthesia, combined anaesthesia or monitored anaesthesia care ASA physical status classification I-III Enrolment and informed consent Exclusion criteria: Absolute and relative indication for rapid sequence induction Registration Dysphagia Renal replacement therapy Fluid restriction therapy Core baseline data - Patients characteristics Pregnancy · Expected need for postoperative mechanical ventilation Randomisation Prior enrolment in this trial. Group 1: Group 2: Group 3: Instructed guideline Usual care Patients are encouraged to drink up to adherence 200 ml clear fluids between 2 h prior to the anaesthesia induction and the call to operation room Call to the operating room Assessments immediately prior to anaesthesia induction: Number of attempts to place an IV-line Blood sample for glucose levels (optional) Patient questionnaires: satisfaction, headache, thirst Vital signs Blinding successfull Immediatly after anaesthesia induction—before start of the surgery: Bronchopulmonary aspiration Blood sample for glucose level (if not already done) Vital signs Use of Vasopressors Blinding successfull

Follow up:

- Bronchopulmonary aspiration
- · PONV assessment
- · Delirium assessment
- · Blinding successfull

## 2 INTRODUCTION

# 2.1 Medical Background

Preoperative fasting guidelines aim to minimize the risk of gastrointestinal regurgitation and bronchopulmonary aspiration with international guidelines recommending clear fluid intake up to 2 h and intake of solid foods and thick liquids up to 6 h prior to anaesthesia induction. Perioperative bronchopulmonary aspiration events are rare and full recovery is typical. Even when fasting guidelines are not followed, perioperative bronchopulmonary aspiration rate has previously been reported as low as 0 % in low-risk populations such as patients undergoing ambulatory cataract surgery or procedures other than endoscopy performed with procedural sedation.

Already three decades ago the adverse consequences of "Nil per os" (NPO) from midnight"-fasting practices have been recognized. Compelling research efforts demonstrating the benefit of allowing free clear fluid intake until 2-3 h preoperatively without increasing bronchopulmonary aspiration rates eventually resulted in changes to international guidelines. While fasting guidelines have changed, extensive preoperative fasting remains common clinical reality. Recently, new discussions have started debating further liberation of preoperative fluid intake restrictions in order to avoid dehydration and improve patient comfort.

## 2.1.1 Dehydration

Contradicting to "primum non nocere" the current practise may harm patients due to dehydration. Dehydration has been shown to worsen the outcome of strokes , raises the risk of infection, may prolong length of stay, lead to thrombosis, ACS or acute kidney injury. Dehydration aggravates pain in general and is discussed as a risk factor for post-lumbar puncture headache from iatrogenic spinal fluid leak .

Parenteral hydration may be considered as a solution, but the risk of infection increases with the time after IV-catheter insertion. Besides the typical risks and complications of an IV-catheter it also reduces patient mobility and contributes to patient stress. This contradicts modern treatment principles like Fast-Track. Furthermore, parenteral hydration does not alleviate dry mouth.

The first principle of 2017 NICE (National Institute of Health and Care Excellence) Recommendations is "Provide intravenous (IV) fluid therapy only for patients whose needs cannot be met by oral or enteral routes [...]". NICE further argues that a significant number of hospitalised patients were dying as a result of infusion of too much or too little fluid. 

According to NICE warning signs for dehydration include but are not limited to:

- systolic blood pressure is less than 100 mmHg
- heart rate is more than 90 beats per minute

#### 2.1.2 Gastric contents

Over the last decade, point-of-care gastric ultrasound has advanced into a well-established and validated tool for evaluation of gastric content in research as well as clinical settings. Gastric ultrasound may guide the assessment of bronchopulmonary aspiration risk and enable risk-adapted clinical decision making.

Preoperative fasting aims to reduce residual gastric volume and increase pH, because higher bronchopulmonary aspiration volume and acidity (e.g. pH < 2.5) are associated with higher mortality in animal models.

This is primarily of relevance for solid food, because drinking 200 ml water raises the gastric pH above pH 4 for a short period of time, as water not only dilutes gastric acid but also has a buffering capacity. The time it takes for oral intake to move on from the stomach depends

largely on composition, calories and volume of the content. This is especially true if pathologies causing delay in gastric emptying are not present. Half of ingested water volume is emptied from the stomach in about 10 min with complete clearance at around 40 min and 80% clearance at 30 min as demonstrated in various studies utilizing isotope activity, MRI imaging as well as gastric ultrasound to examine gastric emptying physiology.

Adherence to NPO does not automatically result in a completely empty stomach. A residual gastric volume of up to 1.8 ml/kg has been demonstrated among patients undergoing elective cholecystectomy and healthy volunteers. In a study examining gastric emptying of water, there was no significant difference of emptying times or residual baseline gastric volume between individuals who remained NPO within 4 h prior to the experiment and those allowed water intake. In accordance with the volume reported in a fasted state, a residual gastric volume above > 1.5 ml/kg has been proposed to indicate higher risk of perioperative bronchopulmonary aspiration.

## 2.1.3 Liberal fasting regime in paediatrics

Elaborate quality improvement initiatives in paediatric anaesthesia have been successful in their efforts to reduce fluid fasting among children, but fear of delay or cancellation of the procedure in case of fluid intake poses a substantial challenge. In some reports in the paediatric population, clear fluid intake was allowed until called to the operating room without observing differences in bronchopulmonary aspiration events or cancellation/postponement of procedures. Multiple renowned anaesthesia societies have issued statements endorsing more liberal oral fluid intake preoperatively in paediatric anaesthesia, like "6-4-1" or "6-4-0" fasting regimes.

Level of similar evidence in the adult population is low. There is no plausible argument why adults should be different than children and teenagers in this matter. In fact, reported bronchopulmonary aspiration rates are higher among children. Of note, recommendations of the Scandinavian Society of Anaesthesiology and Intensive Care Medicine from 2005 permit adults to drink up to 150 ml and children up to 75 ml of clear fluids until 1 hour prior to anaesthesia.

# 2.2 Choice of Comparators

## 2.2.1 Hypothesis

We hypothesize that - compared to standard practice - allowing Patients ≥ 18 years of age undergoing surgery under anaesthesia care to drink clear fluids up to a volume of 200 ml between 2 h prior to anaesthesia and the call to operation room (approximately 30 min prior to anaesthesia induction) will decrease patient thirst and increase patient satisfaction.

## 2.2.2 Risk-Benefit Considerations

Besides the change in preoperative fluid intake, all patients will receive standard perioperative care.

Taking the available data into account it is unlikely for patients in the intervention group to have a substantially higher risk of bronchopulmonary aspiration or a different severity of bronchopulmonary aspiration complications.

Instead, they will be much less likely to experience excessive preoperative fasting durations, which may lead to preoperative dehydration and subsequently contribute to hypotension after anaesthesia induction. This will furthermore improve patient discomfort characterized by increased hunger, thirst, anxiety, sadness, pain, stress and nausea and may even positively influence early postoperative delirium^11 as well as the length of the hospital stay.

In paediatrics and labouring women as well as for adults  allowing clear fluid intake until call to the operating room was already successfully implemented without an increase in bronchopulmonary aspirations being reported.

## 2.2.3 Significance

The growing practise of preoperative fluid consumption ad libitum needs a careful risk-benefit-consideration. It is therefore necessary to assess the benefits. This may pave the way to lift the burden of preoperative thirst from millions of patients yet to come, as the intervention is freely available und rapidly translatable into clinical practice.

# 2.3 Study objectives

## 2.3.1 Primary Objective

To evaluate if allowing patients to drink clear fluids until call to the operating room prior to anaesthesia induction will improve patient thirst compared to allowing clear fluid intake up to 2 h prior to anaesthesia induction.

## 2.3.2 Secondary Objective

We will pilot test the intervention to demonstrate its acceptability and feasibility - in particular we test if the outcome assessment is blindable. The secondary outcomes aim to identify targets for further trials.

# 2.4 Trial design

#### 2.4.1 Trial Design

The study is an outcome assessor blinded randomised trial (RCT) with three parallel treatment arms.

# 3 METHODS: PARTICIPANTS, INTERVENTIONS, OUTCOMES

# 3.1 Study Setting

The study will be conducted at the University Hospital Würzburg enrolling in- and outpatients.

## 3.2 Interventions

Group 1 (control) - Usual care: Fasting instructions as given by anaesthesiologist according to national guidelines (6 h solid meal and thick liquids, 2 h clear fluids).

Group 2 (intervention) - Instructed guideline adherence: As per "Usual care". In addition, the patients will be visited to support and encourage them in drinking clear fluids freely until 2 h before the anticipated anaesthesia induction.

Group 3 (intervention) - Experimental intervention: As per "instructed guideline adherence" with the difference that patients are educated and encouraged to drink up to 200 ml clear fluids between 2 h prior to anaesthesia induction and the call to operation room. Education and information dissemination measures will be taken. Patients receive a container of known volume (e.g. cups, glasses, mugs, bottles with volume marks). From this concludes that patients are allowed to drink up to 100 ml clear fluids every 1 h anaesthesia induction is postponed. Patients may vary their fluid intake to meet this stipulation and their personal needs

e.g. by drinking 100 ml every hour or any other way that does not surpass 200 ml per 2 h (see Fig. 1).

#### 3.2.1 Inclusion criteria

Patients may only be allowed to drink clear fluids up to call to operating room if they fulfill all the following criteria:

- 1. Adult patients (≥ 18 years)
- 2. Undergoing surgery under anaesthesia care: general anaesthesia, regional anaesthesia, combined anaesthesia or monitored anaesthesia care.
- 3. ASA physical status classification I-III

The proportion of patients undergoing general or combined anaesthesia is aimed to exceed 75%.

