## 4 METHODS: ASSIGNMENT OF INTERVENTIONS

## 4.1 Allocation

Sequence Generation: Patients will be randomly assigned to either control or experimental group with a 1:1 allocation per computer generated randomisation schedule using permuted blocks of random sizes. The block sizes will not be disclosed.

Concealment Mechanism: Patients will be randomised using a web-based randomisation system (embedded in REDCap). Allocation concealment will be ensured.

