# 5.5 Sample Size

We plan randomising n=174 patients. n = 174 (55 per group +5% Dropout)

The primary endpoint of this study is thirst immediately before anaesthesia induction. For this purpose, the Bauer Satisfaction Questionnaire is dichotomised - "yes (moderate or strong)" vs. "no thirst". The three groups will be compared with each other. In the control group, based on Bauer et al, 2001, a value of 53% is assumed based on our own experience it is assumed that the experimental intervention (group 3) has a relative effect of 50% and therefore only 26.5% of patients are still thirsty. For group 2 (Instructed guideline adherence) a somewhat weaker effect is assumed. We assume that thirst can be reduced to 30% in this group.

In order to detect these differences between all three groups using a Chi² test with a power of 80%, a total of 165 patients is needed - 55 patients per group.

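### Randomisation and analysis take no account of anaesthesia type, so the induction and recovery pilot endpoints pool differently timed measurements in an uncontrolled mix

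*Combined protocol and SAP*

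**What the plan says.** All places are in the combined protocol and SAP.

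- **Who is eligible (3.2.1).** "Undergoing surgery under anaesthesia care: general anaesthesia, regional anaesthesia, combined anaesthesia or monitored anaesthesia care". The only control on the mix is an intention: "The proportion of patients undergoing general or combined anaesthesia is aimed to exceed 75" per cent. No section gives a quota, an enrolment rule, or a consequence if the aim is missed.
- **Allocation (4.1, with 3.6.1).** REDCap assigns patients by a "computer generated randomisation schedule using permuted blocks of random sizes". No stratification factor is named.
- **Analysis (5.6.2).** A chi-square test for thirst and descriptive statistics are planned. Baseline parameters are to be described by arm, but anaesthesia type is not named among them, and no endpoint is adjusted for type or reported by type.
- **Timing.** Section 3.6.3 starts induction at injection of the hypnotic for general anaesthesia and at injection of the local anaesthetic for local or regional anaesthesia. Section 3.6.5 counts the 2 h to follow-up from extubation or from skin suture respectively.
- **Purpose (2.3.2, 3.5.2).** "The secondary outcomes aim to identify targets for further trials". Section 3.5.2 lists the endpoints concerned as pilot data for later power calculations.

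**The concern.** Anaesthesia type is the one case-mix variable for which the protocol sets a numerical aim, and no stage of the trial controls for it. Two things follow.

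1. **Pooled planning figures.** The 15-minute vasopressor dose and the changes in heart rate and blood pressure are measured after a different event in general and in regional patients. RASS, CAM-ICU and PONV are read at a follow-up timed from a different event. A pooled rate or variance therefore depends on the share of each type that happens to be enrolled. This holds even if the arms are perfectly balanced.
2. **Arm contrasts.** Permuted blocks without strata balance arm sizes, not anaesthesia type within arms. With 58 patients per arm, chance can leave a noticeably different share of regional or monitored-care patients in one arm. If type affects an endpoint, part of the observed arm difference then reflects case mix and not drinking.

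The next trial would take both its choice of outcome and its planning figures from these results.

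**Working it through.** **Inputs from the documents.** 55 evaluable patients per arm and 5% drop-out (5.5); three arms (2.4.1); an aim above 75% general or combined (3.2.1); no strata (4.1).

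**The plan's own figures.** 55 / 0.95 = 57.9, so 58 per arm and 3 × 58 = 174: reproduced. A three-group chi-square test (2 df, alpha 0.05) with 53%, 30% and 26.5% thirsty and 55 per arm has 80.9% power, so the 80% claim also holds.

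**Edge of the aim.** 0.75 × 174 = 130.5. Exceeding 75% needs at least 131 general or combined patients, which leaves at most K = 43 others (43 / 174 = 24.7%).

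**Chance imbalance without strata.** Spread K such patients at random over three arms of 58 (multivariate hypergeometric). A gap of 6 patients is 6 / 58 = 10.3 percentage points; a gap of 9 is 9 / 58 = 15.5 points.

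| K | Given pair, gap ≥ 6 | Given pair, gap ≥ 9 | Largest of three gaps ≥ 6 | Largest of three gaps ≥ 9 |
|---|---|---|---|---|
| 20 | 0.11 | 0.01 | 0.25 | 0.03 |
| 43 | 0.24 | 0.07 | 0.47 | 0.16 |
| 60 (aim missed) | 0.28 | 0.10 | 0.52 | 0.22 |

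The pair columns apply to the hypothesised contrast, group 3 against group 1.

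**What an imbalance does to a binary endpoint (assumed rates).** Shift = imbalance × difference between types. The documents give no rates by type. Assume that 50% of general or combined patients and 10% of the others receive a vasopressor.

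- Shift from a 10-point imbalance: 0.10 × (0.50 − 0.10) = 4 points.
- Overall rate with 25% others: 0.75 × 0.50 + 0.25 × 0.10 = 0.40.
- Standard error of an arm difference: √(2 × 0.40 × 0.60 / 58) = 9.1 points.
- With the type component removed, the within-type variance is 0.75 × 0.25 + 0.25 × 0.09 = 0.21 and the standard error is √(2 × 0.21 / 58) = 8.5 points.

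**What it does to a continuous endpoint (assumed type effect of 0.5 to 1.5 SD).** A 15.5-point imbalance shifts the contrast by 0.155 × 0.5 = 0.08 SD to 0.155 × 1.5 = 0.23 SD. The standard error is about √(2 / 58) = 0.19 SD. In simulation (58 per arm, 25% others), the false-positive rate of an unadjusted test, given that imbalance, is 6%, 9% and 14% for effects of 0.5, 1.0 and 1.5 SD. Given an 8.6-point imbalance it stays near 5%. Over all randomisations, at 1.5 SD, it is 4.8%.

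**With strata.** Within a stratum the gap between arms is limited to one incomplete block. Block sizes are undisclosed. If they are 3, 6 or 9, the most two arms can differ is 1, 2 or 3 patients, that is 1.7, 3.4 or 5.2 points of 58. If the analysis then ignores the stratum, the test becomes conservative: with forced balance and a 1.5 SD effect, the simulated false-positive rate falls to 1.9%. Stratification should therefore be paired with adjustment.

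**The case against.** The strongest reply is that unstratified allocation is a legitimate choice in a 174-patient pilot and that the practical effect is small. Most of this stands.

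- Randomisation keeps every contrast unbiased on average and the overall false-positive rate near 5%.
- In the vasopressor illustration the 4-point shift is under half of the 9.1-point standard error. Removing the type component only lowers that error to 8.5. A contrast too imprecise to guide the choice of outcome remains imprecise.
- The shift becomes material only with an imbalance of about 15 points and a strong type effect. At the edge of the aim, a gap that large has probability 0.07 for a given pair.
- Thirst is measured before induction, so the anaesthetic cannot act on it directly.

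A reader might infer three stronger things that the documents do not support. First, that these endpoints depend heavily on general anaesthesia, or sit near their floor in other patients: no section gives a rate by type. Second, that the 75% aim proves that the sponsor regards type as prognostic: section 3.2.1 gives no reason for it. Third, that the aim must become a hard limit of 43 patients: admitting all four types is deliberate, and a limit would turn away eligible patients in a single-centre trial with three months to recruit.

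The reply does not answer the first part of the concern. The different clocks are in the protocol's own text, and pooled figures mix them whether or not the arms are balanced. Reporting by type could be done without changing the randomisation, but section 5.6.2 does not plan it.

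**Conclusion.** The point holds in a limited form. The plan neither stratifies by anaesthesia type nor analyses by it, while it times induction and follow-up differently for general and regional anaesthesia. Pooled pilot figures for the induction and recovery endpoints therefore depend on a case mix that nothing controls.

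For arm contrasts, the consequence is chance imbalance and some lost precision: a gap of at least 10 points between a given pair of arms has probability 0.24 at the edge of the aim and 0.11 with 20 such patients. It is not bias on average, does not inflate the overall error rate, and does not touch the primary endpoint directly. Its effect on any endpoint rests on an assumed difference between types, and over the range tried it runs from negligible to about one standard error. The reason to act is that the remedy is cheap and gives the next trial cleaner planning figures, not that the present contrasts are invalid.

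**What to change.** 1. **Section 4.1:** stratify the REDCap randomisation by planned anaesthesia type, general or combined against regional or monitored care. Keep random block sizes within each stratum.
2. **Section 5.6.2:** report vasopressor dose, change in heart rate and blood pressure, RASS, CAM-ICU and PONV for the general or combined stratum as well as overall. Adjust the arm contrasts for planned type.

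No cap on regional or monitored-care patients is needed.

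**Cost.** One two-level field in REDCap, which should be available from the premedication visit already filed under section 1.2.1, and a sentence in each of two sections. The sample size stays at 174. Randomisation can take place up to 28 days before surgery, so a few patients will change technique afterwards; they stay in their planned stratum, which slightly weakens the balance achieved.
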